In a randomized trial of olaparib 400 mg (capsule) twice daily as maintenance monotherapy (53 patients) compared to placebo (43 patients) in patients with platinum sensitive, relapsed, high-grade serous ovarian cancer following treatment with 2 or more platinum-containing regimens, the median duration on treatment with olaparib was 11.1 months for patients with a gBRCA mutation compared to 4.4 months for patients with gBRCA mutation on placebo. Adverse reactions led to dose interruptions in 26% of those receiving olaparib and 7% of those receiving placebo; dose reductions in 15% of olaparib and 5% of placebo patients; and discontinuation in 9% of olaparib and 0% in placebo patients. One (2%) patient on olaparib died as a result of an adverse reaction.

Adverse Reactions Reported in $\geq 20\%$ of Patients with gBRCA-Mutated Ovarian Cancer in the Randomized Trial were anemia, abdominal pain/discomfort, decreased appetite, nausea, vomiting, diarrhea, dyspepsia, fatigue/asthenia, nasopharyngitis, upper respiratory infection, arthralgia, myalgia, back pain, headache, cough and dermatitis/rash. Laboratory Abnormalities observed were decrease in hemoglobin, absolute neutrophil count, platelets, mean corpuscular volume elevation, and increase in creatinine.

Myelodysplastic syndrome/Acute Myeloid Leukemia (overall 22 out of 2618 patients i.e. 1%) and pneumonitis ($< 1\%$) occurred in patients exposed to olaparib, and some cases were fatal.

Potential overlapping toxicity between olaparib, durvalumab, and tremelimumab are: diarrhea, enterocolitis, myalgia, arthralgia, fatigue, and rash. However, based on published studies, anti-CTLA-4 appears to be associated with more frequent and severe side effects.

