Serum Chemistry ^{18, 10}		X	X		X	X
CA-125 level ¹⁰		X	X ²⁰		X ²⁰	
Obtain archived tumor tissue for PD-L1 assay (see section 8.5.1.1 for further detail)	X					
Hepatitis B & C; HIV		X				
Serum hCG ³		X	X ³			
Thyroid function tests ^{9, 10}		X	X ²⁰			
Urinalysis ^{11, 10}		X	X		X	
Coagulation parameters ¹²		X				

Evaluation¹	Pre-Screening (Day -42 to Day -1)	Screening (Day -28 to Day -1)	All assessments to be performed pre-infusion unless stated otherwise.			End of Treatment Visit¹⁹ (± 7 days)
			Cycle 1 Day 1	Cycle 1 Day 15 (± 3 days)	Cycle 2-13, Day 1 (± 3 days)	
PAXgene® RNA tube (whole blood sample for mRNA/miRNA profiling) ¹³			X		X ¹³	
Blood for immune monitoring ¹⁴			X	X	X	
Blood for circulating soluble factors ¹⁵			X		X ¹⁵	
Imaging/Other Procedures						
Brain MRI		X ²				
12-Lead Electrocardiogram (see section 8.3.3 for further detail) ⁷		X ⁷	X ⁷		X ⁷	
Tumor Biopsy					X ¹⁶	

Tumor/Disease Assessment by irRECIST (CT or MRI)		X ¹⁷			X ¹⁷	X ¹⁷
Evaluation ¹	Pre-Screening (Day -42 to Day -1)	Screening (Day -28 to Day -1)	All assessments to be performed pre-infusion unless stated otherwise.			End of Treatment Visit ¹⁹ (± 7 days)
			Cycle 1 Day 1	Cycle 1 Day 15 (± 3 days)	Cycle 2-13, Day 1 (± 3 days)	
Study Drug Administration						
Durvalumab administration			X		X	
Tremelimumab administration			X		X ⁴	
Olaparib administration			X ----- BID continuous dosing, up to 1 year-----			

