In case of clinically significant ECG abnormalities, including a QTcF value ≥ 470 ms, 2 additional 12-lead ECGs should be obtained over a brief period (e.g. 30 minutes) to confirm the finding.

8. For AEs/SAEs reported during pre-screening, additional information such as medical history and concomitant medications may be needed.
9. TSH level will be obtained at screening, on Cycle 1 Day 1 and as clinically indicated. Free T3 and free T4 level will only be measured if TSH is abnormal. Thyroid function tests should also be measured if there is clinical suspicion of an adverse event related to the endocrine system. Refer to Section 8.3.4.
10. Refer to Table 6 in Section 8.3.4. If screening laboratory assessments are performed within 3 days prior to Cycle 1 Day 1, they do not need to be repeated. Results for safety bloods must be available and reviewed before commencing an infusion.
11. Refer to Table 8 in Section 8.3.4. Urinalysis to be performed at screening, on day 1 of each cycle and as clinically indicated.
12. Prothrombin time, APTT and INR to be performed at screening and as clinically indicated. Refer to Section 8.3.4.
13. PAXgene® RNA tube will be collected on day 1 of cycles 1 & 2 (± 3 days) and day 1 of cycles 3, 5, 7, 9, 11, & 13 (± 7 days). Refer to Section 8.4.2.2.
14. Blood for immune monitoring will be collected on Cycle 1 Day 1, Cycle 1 Day 15, and Day 1 of cycles 2-13. Refer to Section 8.4.2.1.
15. Refer to Section 8.4.2.3. Blood for Circulating Soluble Factors will be collected on Cycle 1 Day 1, Cycle 2 Day 1 and Cycle 4 Day 1 only.
16. Tumor biopsy will be performed on cycle 4 day 1 (± 7 days and if clinically appropriate) after completion of CT scan for biopsy site determination or at the time of progression (if clinically appropriate). Refer to Section 8.5.1.2.

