17. CT (preferred) or MRI scans, preferably with IV contrast, are collected during screening (for baseline), as close to and prior to initiation of study treatment. Timing of on-treatment CT/MRI scans is pre-dose C4D1 (± 7 days) for biopsy site determination and every 3 cycles thereafter (i.e. Day 1 of Cycles 7, 10, 13 ± 7 days) or as clinically indicated until progressive disease or off-study. Response according to irRECIST criteria (irCR, irPR) requires a confirmatory scan preferably at the next regularly scheduled imaging visit and no earlier than 6 weeks after the prior assessment of CR, PR, or SD is deemed by irRECIST. End of Treatment disease assessment does not need to be repeated if performed within 28 days prior to end of treatment.
18. Refer to Table 7 for details.
19. Refer to Appendix H and Appendix I for follow-up visits.
20. Results from CA-125 and thyroid function test do not need to be available prior to dosing patient on dosing days.

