10.2.1 Durvalumab + Tremelimumab AESIs

AESIs for durvalumab and tremelimumab include but are not limited to events with a potential inflammatory or immune-mediated mechanism and which may require more frequent monitoring and/or interventions such as steroids, immunosuppressants and/or hormone replacement therapy. These AESIs are being closely monitored in clinical studies with durvalumab monotherapy and combination therapy. An immune-related adverse event (irAE) is defined as an adverse event that is associated with drug exposure and is consistent with an immune-mediated mechanism of action and where there is no clear alternate etiology. Serologic, immunologic, and histologic (biopsy) data, as appropriate, should be used to support an irAE diagnosis. Appropriate efforts should be made to rule out neoplastic, infectious, metabolic, toxin, or other etiologic causes of the irAE.

If the Investigator has any questions in regard to an adverse event (AE) being an irAE, the Investigator should promptly contact the Study Sponsor.

AESIs observed with durvalumab and tremelimumab include:

- Diarrhea / Colitis and intestinal perforation
- Pneumonitis / ILD
- ALT/AST increases / hepatitis / transaminase increases / hepatotoxicity
- Neuropathy / neuromuscular toxicity (i.e. events of encephalitis, peripheral motor and sensory neuropathies, Guillain-Barré, and myasthenia gravis)
- Endocrinopathy (i.e. events of hypophysitis / hypopituitarism, adrenal insufficiency, and hyper- and hypothyroidism and type I diabetes mellitus)

- Rash / Dermatitis
- Nephritis / Blood creatinine increases
- Pancreatitis (or labs suggestive of pancreatitis - increased serum lipase, increased serum amylase)
- Myocarditis
- Myositis / Polymyositis
- Intestinal Perforation
- Other inflammatory responses that are rare / less frequent with a potential immune-mediated etiology include, but are not limited to, pericarditis, sarcoidosis, uveitis and other events involving the eye (e.g., keratitis and optic neuritis) skin (e.g., scleroderma, vitiligo and pemphigoid) , hematological (e.g., hematological anemia and immune thrombocytopenic purpura) and rheumatological events (polymyalgia rheumatic and autoimmune arthritis), vasculitis, non-infectious meningitis and non-infectious encephalitis.

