		
 If toxicity improves to Grade ≤ 1 or baseline, then resume drug/study regimen after completion of steroid taper. 	
 Consider moderate-strength topical steroid. If no improvement of rash/skin lesions occurs within 3 to 5 days or is worsening despite symptomatic treatment and/or use of moderate strength topical steroid, consider, as necessary, discussing with study physician and promptly start systemic steroids such as prednisone 1 to 2 mg/kg/day PO or IV equivalent. Consider skin biopsy if the event is persistent for >1 to 2 weeks or recurs.
	Grade 3 or 4	
For Grade 3: Hold study drug/study regimen until resolution to Grade ≤ 1 or baseline. If temporarily holding the study drug/study regimen does not provide improvement of the Grade 3 skin rash to Grade ≤ 1 or baseline within 30 days, then permanently discontinue study drug/study regimen.
 
For Grade 4: Permanently discontinue study drug/study regimen.
	
For Grade 3 or 4:
 
 Consult Dermatology. Promptly initiate empiric IV methylprednisolone 1 to 4 mg/kg/day or equivalent. Consider hospitalization. Monitor extent of rash [Rule of Nines]. Consider skin biopsy (preferably more than 1) as clinically feasible. Once the patient is improving, gradually taper steroids over ≥ 28 days and consider prophylactic antibiotics, antifungals, and anti-PCP treatment (refer to current NCCN guidelines for treatment of cancer-related infections).^a Consider, as necessary, discussing with study physician.
Endocrinopathy (e.g., hyperthyroidism, thyroiditis, hypothyroidism, Type 1 diabetes mellitus hypophysitis, hypopituitarism, and adrenal insufficiency; exocrine event of amylase/lipase increased also included in this section)	Any Grade (depending on the type of endocrinopathy, refer to NCI CTCAE v4.03 for defining the CTC grade/severity)	General Guidance	
For Any Grade:
 
 Consider consulting an endocrinologist for endocrine events. Consider, as necessary, discussing with study physician. Monitor patients for signs and symptoms of endocrinopathies. Non-specific symptoms include headache, fatigue, behavior changes, changed mental status, vertigo, abdominal

Specific Immune-mediated Reactions			
Adverse Events	Severity Grade of the Event (NCI CTCAE version 4.03)	Dose Modifications	Toxicity Management

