			
pain, unusual bowel habits, polydipsia, polyuria, hypotension, and weakness.
 
 Patients should be thoroughly evaluated to rule out any alternative etiology (e.g., disease progression including brain metastases, or infections). Depending on the suspected endocrinopathy, monitor and evaluate thyroid function tests: TSH, free T3 and free T4 and other relevant endocrine and related labs (e.g., blood glucose and ketone levels, HgA1c). For asymptomatic elevations in serum amylase and lipase $>\text{ULN}$ and $<3 \times \text{ULN}$, corticosteroid treatment is not indicated as long as there are no other signs or symptoms of pancreatic inflammation. If a patient experiences an AE that is thought to be possibly of autoimmune nature (e.g., thyroiditis, pancreatitis, hypophysitis, or diabetes insipidus), the investigator should send a blood sample for appropriate autoimmune antibody testing.
	Grade 1	No dose modifications.	
For Grade 1 (including those with asymptomatic TSH elevation):
 
 Monitor patient with appropriate endocrine function tests. For suspected hypophysitis/hypopituitarism, consider consultation of an endocrinologist to guide assessment of early morning ACTH, cortisol, TSH, and free T4; also consider gonadotropins, sex hormones, and prolactin levels, as well as cosyntropin stimulation test (though it may not be useful in diagnosing early secondary adrenal insufficiency). If $\text{TSH} < 0.5 \times \text{LLN}$, or $\text{TSH} > 2 \times \text{ULN}$ or consistently out

Specific Immune-mediated Reactions			
Adverse Events	Severity Grade of the Event (NCI CTCAE version 4.03)	Dose Modifications	Toxicity Management
			
of range in 2 subsequent measurements, include free T4 at subsequent cycles as clinically indicated and consider consultation of an endocrinologist.

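### TSH is scheduled only before the first dose, so on-treatment thyroid testing is for-cause until Day 30 after the last dose although thyroid events are listed AESIs (low priority, cheap to improve)

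*Combined protocol and SAP*

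**What the plan says.** Footnote 9 to Table 5 (Section 8.2) fixes the thyroid tests: "TSH level will be obtained at screening, on Cycle 1 Day 1 and as clinically indicated". It adds testing on clinical suspicion of an endocrine event, with free T3 and free T4 only if TSH is abnormal. The grid agrees. The row "Thyroid function tests" is marked at Screening and Cycle 1 Day 1 and is blank at Cycle 1 Day 15, Day 1 of Cycles 2-13 and End of Treatment. The synopsis and Sections 8.1.2 and 8.1.3 match.

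Table 5 assessments are pre-infusion unless stated otherwise, so both samples are baseline values. Footnote 10 lets a site skip the second if screening bloods were taken within 3 days. Footnote 20 says "Results from CA-125 and thyroid function test do not need to be available prior to dosing patient on dosing days". The next scheduled test is on Day 30 after the last dose (Appendices H and I).

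Section 10.2.1 includes "adrenal insufficiency, and hyper- and hypothyroidism and type I diabetes mellitus" among the endocrine AESIs. Appendix G (Endocrinopathy) covers Grade 1 cases "including those with asymptomatic TSH elevation". For TSH that is consistently out "of range in 2 subsequent measurements, include free T4 at subsequent cycles as clinically indicated", it also advises considering an endocrinology consultation. Table 10 (Section 8.4.2) lists 14 thyroid samples over the year.

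**The concern.** A patient can receive up to 13 durvalumab and 4 tremelimumab doses, with 4 more tremelimumab doses allowed after progression, and have no scheduled thyroid test after the first dose until treatment is over. Testing prompted by symptoms cannot find dysfunction that has none.

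Symptoms are also a weak prompt in this trial. Appendix G says "Non-specific symptoms include headache, fatigue, behavior changes, changed mental status". Section 1.3.2.4 lists fatigue again among the shared effects of the three drugs: "Potential overlapping toxicity between olaparib, durvalumab, and tremelimumab are: diarrhea, enterocolitis, myalgia, arthralgia, fatigue, and rash". A site could reasonably put fatigue down to olaparib and not order TSH.

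What is at stake is safety detection and even ascertainment. In a multicenter study, the reported thyroid AESI rate would depend partly on how readily each site orders the test. The Appendix G actions for an asymptomatic abnormality can start only once someone has tested.

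**Working it through.** **1. Table 10 against the schedule.** Table 10 is arithmetically sound: 56 + 56 + 56 + 4 + 20 + 1050 + 15 = 1257 mL, and 14 + 14 + 14 + 1 + 8 + 15 + 3 = 69 samples. Its thyroid row is 14 × 4 mL = 56 mL. Table 5 schedules 1 (Screening) + 1 (Cycle 1 Day 1) = 2 samples, or 8 mL. Adding Day 1 of Cycles 2-13 gives 1 + 1 + 12 = 14.

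Table 10 departs from the schedule elsewhere too:
- Chemistry and hematology: 1 + 1 + 12 + 1 (End of Treatment) = 15 draws scheduled, 14 listed.
- Immune monitoring: 6 × 10 + 4 = 64 mL in Section 8.4.2.1, 70 mL listed.

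**2. Length of the gap.** Inputs are the 28-day cycle and the Day 30 test. Counted from the last of n durvalumab doses, without holds, the gap from Cycle 1 Day 1 is 28(n-1) + 30 days:

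| n | gap (days) |
|---|---|
| 2 | 58 |
| 4 | 114 |
| 7 | 198 |
| 10 | 282 |
| 13 | 366 |

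Appendices H and I count from the last dose of any of the three drugs. Thirteen cycles of daily olaparib end near day 13 × 28 = 364, which gives 364 + 30 = about 394 days.

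**3. Illustrative average gap in Phase II.** Assumptions: constant hazard, a month of 365.25/12 days, and the Section 12.4 rates, with 18 resistant and 9 sensitive patients. The null is 0.55 at 3 months and 0.65 at 6 months; the alternative is 0.75 and 0.80. Expected Day 1 visits in Cycles 2-13 are the sum of S(28k) for k = 1 to 12, where S is the probability of still being progression-free.

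- Null: 4.42 resistant and 8.02 sensitive. (18 × 4.42 + 9 × 8.02)/27 = 5.6 visits; mean gap 30 + 28 × 5.62 = 187 days.
- Alternative: 7.08 and 9.67. The same formula gives 7.9 visits and 252 days.

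That stops treatment at the moment of progression. Scheduled scans come only at Cycles 4, 7, 10 and 13. If treatment stops at those scans instead:

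- Null: 5.42 and 8.59, giving 6.5 visits and 211 days.
- Alternative: 7.77 and 10.02, giving 8.5 visits and 269 days.

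Treatment past progression lengthens these figures, and early toxicity stops shorten them.

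**4. How common the events might be.** Section 1.3.2.3 gives 11.5% hypothyroid events on durvalumab plus tremelimumab, with 0.2% at Grade 3 or higher. If those rates applied here (an assumption, since olaparib was not part of those regimens), 27 × 0.115 = 3.1 patients and 27 × 0.002 = 0.05. How many of these for-cause testing would miss is not known.

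**5. The lighter option.** With TSH at Cycles 4, 7, 10 and 13, tests during treatment are 3 × 28 = 84 days apart. A patient whose last durvalumab dose is at Cycle 3, 6, 9 or 12 waits 56 + 30 = 86 days, before visit windows and holds.

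**The case against.** The strongest reply is that for-cause testing is a deliberate choice, stated consistently, and that nothing in the protocol requires TSH at each cycle. There are also real safeguards. Footnote 1 allows any assessment that management requires. Examination, weight, ECOG status and adverse events are recorded on Day 1 of every cycle. Section 10.2.3 asks sites to watch for immune-related events. Uncontrolled thyroid dysfunction is excluded at entry, and Appendix A provides for weekly or bi-weekly safety calls. Most events would be low grade, and Appendix G manages isolated hypothyroidism without stopping study drug. All of this stands and keeps the priority low. It does not close the gap, because each safeguard depends on symptoms or judgement and cannot reliably find asymptomatic dysfunction.

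A reader might go further and infer from Table 10's 14 samples, or from Appendix G's advice on repeated TSH values, that testing at each cycle was intended and then dropped by mistake. The documents do not show this. Table 10 is a volume estimate that misses the schedule in other rows, and Appendix G is a generic guideline, partly led by suspicion. A reader might also infer that any abnormality followed up under Appendix G is necessarily a recordable adverse event. Section 10.1.1.3 requires it to be clinically significant as well as to need active management, so it could be recordable but need not be.

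**Conclusion.** The concern holds as a cheap improvement to consider, at low priority. The schedule facts are certain: no thyroid test is scheduled between Cycle 1 Day 1 and Day 30 after the last dose. For a patient completing the year without holds, that is 366 days from the last durvalumab dose rule or about 394 days counting from olaparib. The modelled mean gaps of about 187 to 252 days, or 211 to 269 days with scan-timed stopping, rest on constant hazard at the protocol's own rates and only illustrate scale.

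The likely consequence is limited to under-detection or late detection of asymptomatic and low-grade thyroid AESIs, and uneven ascertainment between sites. Its size cannot be estimated from the documents. Alpha, power and the primary PFS endpoint are unaffected. Separately, Table 10 and Table 5 disagree on the number of thyroid samples, and one of them needs editing whichever policy is chosen.

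**What to change.** In Table 5, add TSH, with free T3 and free T4 if abnormal, on Day 1 of Cycles 2-13. Amend footnote 9 to match and apply footnote 20 to the new cells so that dosing does not wait for the result. The count then matches Table 10, and the 1257 mL total does not change. A lighter option is TSH at Cycles 4, 7, 10 and 13 only; Table 10's thyroid count would then need to be 2 + 4 = 6. If neither is adopted, correct Table 10 to 2 thyroid samples and 8 mL, with totals of 69 - 12 = 57 samples and 1257 - 48 = 1209 mL.

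The main option costs up to 12 extra TSH assays per patient in the initial treatment year (12 × 27 = 324 for Phase II), on days when chemistry and hematology are already drawn. Retreatment follows the same schedule and would add more. Reflex free T3 and free T4 tests, repeat tests and consultations after abnormal results come on top. Because Phase I is complete, thyroid ascertainment will differ between patients treated before and after the change; the safety report should state which schedule applied to whom.
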